Positive subjective effects of nicotine will be assessed with the “Like the Drug Effects” and “Good Drug Effects” items from the DEQ, consistent with the FDA Guidance on abuse potential assessment (10). These items have been shown to correlate with the abuse potential of drugs of abuse. Effects will be tested using linear mixed effects models with peak change on each DEQ item as a response variable, cigarette-preference (menthol vs. non-menthol) as a between-subject factor, nicotine delivery condition as a within-subject factor and their interaction. Period effects will be controlled for by including test day as an additional predictor in the models. Random effects for subject and condition within subject will be used to account for correlations between repeated measures. Because of the potential skewed distributions of the subjective effects data, transformations will be applied as necessary. We will evaluate the main and interactive effects of menthol cigarette preference and delivery rate. We anticipate statistically significant main effects of menthol-preference, nicotine delivery rate and a significant interaction between menthol-preference and nicotine delivery rate. To better understand the dose effects of nicotine delivery rate and whether they are moderated by menthol preference, we will construct specific contrasts among the four doses to test whether there is an indication of significant linear, quadratic, linear on log-scale or sigmoidal dose-response relationships across, or within menthol-preference groups. The possible dose-response curves identified by the specific mean contrasts will be compared by fitting linear and non-linear (as necessary) dose-response models with continuous dose and selecting the best-fitting model by the Akaike’s Information Criterion (AIC).

To test for an effect of delivery rate on smoking urges, assessed by the BQSU (Factor 1 and 2) scores, we will use similar modeling approach described for subjective effects but we will also include time as a within-subject factor with outcomes for minute 0, 10, 30, 60 and 120. We anticipate a significant main effect of menthol-preference, nicotine delivery rate and potentially a significant interaction between menthol-preference and nicotine delivery rate.

Rationale for sample size:

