The study will have 80% power to detect large effect sizes ($f=0.4$) for the main effect of menthol with 31 individuals per group at 0.025 significance level (Bonferroni-adjusted for two outcome measures) for each hypothesis. Our previous study showed large magnitude effects of preference for mentholated cigarettes on feeling good and stimulated effects ($d=0.8$ or larger, corresponding to $f=0.4$ or larger). Our pilot data also showed large effects of nicotine ($f>0.6$) and the rate of infusion effects are expected to be similarly strong (42, 48, 54, 83). With 28

individuals per group we have 80% power to detect effect sizes of this magnitude ($f>0.5$) for the within-subject effect of nicotine delivery rate and in the interaction between nicotine delivery rate and menthol. To account for 20% drop-out rate, we will recruit 35 participants for each group.

11. Risks and benefits:

Potential risks

There are potential risks, discomforts and inconveniences associated with the participation in this study. These may be due to nicotine administration, blood drawing, and other study procedures.

- 1) The administration of nicotine may cause cardiovascular, autonomic, and gastrointestinal complications. Large doses of nicotine may cause nausea, vomiting, abdominal pain, hypersalivation, diarrhea, dizziness, confusion, hearing and vision problems, syncope, seizures, hypotension, irregular pulse, and death. However, these toxic effects occur at doses 10-20 times that which will be used in our study. Other potential risks from this study include administering a drug that has addictive potential. However, since only subjects with a history of cigarette use are to be included, we will not be exposing subjects to the risks of nicotine for the first time. Additionally, we are not enrolling subjects who are seeking treatment to quit smoking. Over the last 5 years, we have administered nicotine intravenously to more than 100 smokers and have not encountered any adverse events from nicotine.
- 2) Blood Drawing: Subjects will have less than 300 ml of blood drawn as a result of their participation in the study. Blood drawing can cause some pain and may result in bruising.

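### Holm's step-down in place of plain Bonferroni for the two outcome measures would keep the 5% family-wise error and, if both DEQ items carry the planned effect, add about 3 to 6 points of power per item for the menthol main effect

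*Combined protocol and SAP*

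**What the plan says.** The only statement on multiplicity is in the sample-size rationale of section 10: "The study will have 80% power to detect large effect sizes ($f=0.4$) for the main effect of menthol with 31 individuals per group", and this is "at 0.025 significance level (Bonferroni-adjusted for two outcome measures) for each hypothesis". The two outcome measures are not named there.

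The analysis text of the same section points to the likely pair: "Positive subjective effects of nicotine will be assessed with the “Like the Drug Effects” and “Good Drug Effects” items from the DEQ". It fits "linear mixed effects models with peak change on each DEQ item as a response variable". It gives no significance level, testing order or step-down rule. Smoking urges are analysed on BQSU Factors 1 and 2, which could form a second pair.

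On numbers, the rationale ends with "To account for 20% drop-out rate, we will recruit 35 participants for each group", whereas section 8 gives 35 per group as the number of completers.

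**The concern.** Plain Bonferroni holds each item to 0.025 even after the other has been rejected. Holm's procedure starts at the same 0.025 for the smaller p-value, then releases the full 0.05 to the remaining one. The family-wise guarantee is the same, and no result that is significant under Bonferroni is lost.

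The second item matters here. Hypothesis 1B in section 4 predicts greater responses in non-menthol smokers on the outcomes as a set, and section 10 anticipates a significant menthol main effect. If both items do respond, Bonferroni discards some second-item findings that could be claimed at the same error rate.

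**Working it through.** **Inputs.** From section 10: f = 0.4, which is d = 0.8 for two equal groups (f = d/2); 31 per group; 0.025 per outcome. Group sizes of 28 (35 × 0.8, after the stated drop-out) and 35 (the completer goal in section 8) are also run. The documents do not state sidedness; two-sided tests are assumed. They do not give the correlation r between the two items, so r is varied from 0 to 0.9.

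**Step 1: reproduce the plan's figure.** For a two-sample t-test with n per group, the noncentrality is d × √(n/2) = 0.8 × √(31/2) = 3.15, on 60 degrees of freedom. Power by the noncentral t distribution:

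| n per group | at 0.025 | at 0.05 |
|---|---|---|
| 28 | 75.2% | 83.6% |
| 31 | 80.0% | 87.3% |
| 35 | 85.2% | 91.0% |

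The stated 80% at 31 per group is confirmed.

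**Step 2: what Holm adds.** An item gains only when its own p-value lies between 0.025 and 0.05 and the other item's is at or below 0.025. So

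per-item gain = P(0.025 < p₁ ≤ 0.05 and p₂ ≤ 0.025).

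The gain cannot exceed 87.3 − 80.0 = 7.3 points at 31 per group. With independent items it is 0.073 × 0.800 = 0.058, or 5.8 points. With equal effects, the gain in power to reject both items is twice the per-item gain.

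**Step 3: correlated items, d = 0.8 on both, 31 per group.** Simulation of two correlated t statistics (gains taken before rounding):

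| r | Per item, Bonferroni → Holm | Gain (points) | Both items, Bonferroni → Holm | Gain (points) | At least one (either method) |
|---|---|---|---|---|---|
| 0 | 80.0 → 85.8% | 5.8 | 64.0 → 75.7% | 11.7 | 96.0% |
| 0.3 | 80.0 → 85.2% | 5.2 | 66.5 → 77.0% | 10.5 | 93.4% |
| 0.5 | 80.0 → 84.9% | 4.9 | 68.6 → 78.3% | 9.7 | 91.4% |
| 0.7 | 80.0 → 84.3% | 4.3 | 71.1 → 79.7% | 8.6 | 88.9% |
| 0.8 | 80.0 → 83.9% | 3.9 | 72.7 → 80.6% | 7.9 | 87.2% |
| 0.9 | 80.0 → 83.4% | 3.4 | 74.9 → 81.7% | 6.7 | 85.1% |

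The simulated row at r = 0 agrees with the hand calculation in step 2.

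**Step 4: other group sizes, same effects.** Per-item power:

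| n per group | Bonferroni | Holm, r = 0.9 to 0 | Gain (points) |
|---|---|---|---|
| 28 | 75.2% | 79.0 to 81.6% | 3.8 to 6.3 |
| 35 | 85.2% | 88.0 to 90.1% | 2.8 to 5.0 |

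**Step 5: unequal effects, 31 per group, r from 0 to 0.9.**
- First item d = 0.8, second d = 0.4: the stronger gains 1.8 points at r = 0, falling to 0 at r = 0.9. The weaker gains 7.9 to 9.8 points, from a Bonferroni power of about 24%.
- First item d = 0.8, second with no effect: the first gains at most 0.2 points.

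**Step 6: error control.** With no effect on either item, the chance of any false rejection is the same under both procedures and is highest at r = 0, at 4.95%. With d = 0.8 on one item only, Holm falsely rejects the null item in at most 4.5% of trials. Both are below 5%.

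**The case against.** **Bonferroni is valid and meets its target.** This stands. The plan reaches its 80% at 31 per group, and Bonferroni gives simple simultaneous intervals. A reader might infer that the error control is faulty or that the choice leaves the trial underpowered; the documents support neither. Whether 35 per group is a recruitment figure or a completer figure is a separate matter and adds no weight here.

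**The text may not bind the analysis to Bonferroni.** This stands in part. The 0.025 appears only in the sample-size rationale, and sizing at 0.025 is compatible with Holm's first step. But no step-down rule is written anywhere, so Bonferroni is the only control on record. That the pair means the two DEQ items is the natural reading, not a stated one.

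**The gain depends on both items responding.** This stands. The prior evidence that section 10 cites for a large menthol effect concerns feeling good and feeling stimulated, not drug liking. A reader might infer that power is lost on both items whatever the truth; step 5 shows otherwise.

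**Liking and good effects probably move together.** A reader might infer that this is where Holm helps most. It is the reverse: with equal effects the gain falls from 5.8 points at r = 0 to 3.4 at r = 0.9.

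**Success on both items is not a stated criterion.** Correct. The chance of at least one finding is identical under the two procedures, so both-item power is supporting information only.

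**Conclusion.** The point holds as a low-cost improvement. For the test decisions, Holm's advantage needs no assumption about the data: it makes the same or more rejections at the same 5% family-wise error. Its size does need assumptions. With d = 0.8 on both items and two-sided tests, per-item power for the menthol main effect rises by about 3 to 6 points at 31 per group, 3 to 5 at 35 and 4 to 6 at 28. At 31 per group, power to reject both items rises by about 7 to 12 points. At correlations up to about 0.3, Holm with 31 per group does as well per item as Bonferroni with 35 (85.2%).

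If the items correlate at 0.8 to 0.9, expect 3 to 4 points per item at 31 per group. If one item has a weak effect, nearly all the gain goes to that item; if it has none, the responding item gains almost nothing.

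These figures treat the menthol main effect as a two-group comparison. They should not be read across to the delivery-rate effect or the interaction, for which nothing was computed.

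**What to change.** In section 10:

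1. Name the two outcomes in each hypothesis family. If BQSU Factors 1 and 2 are a second family, say so.
2. Put the testing rule in the analysis text, replacing the Bonferroni wording. For example: within each family, the smaller of the two p-values is compared with 0.025; if it is significant, the other is compared with 0.05; if it is not, neither is declared significant.
3. Keep the sizing at 0.025 as the conservative first step, and report per-item and both-item power under Holm over a range of correlations, including a case with unequal effects.

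The cost is wording, settled before unblinding; sample size and conduct do not change. The one real downside is that confidence intervals matching Holm's decisions are less simple than Bonferroni intervals. The plan promises no simultaneous intervals, so it should state which intervals will be reported.

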One hundred smokers will be recruited from the New Haven area through newspaper, and radio advertisements and fliers. The study will be described over the telephone. Subjects will be given a brief tobacco use history and medical screening questionnaire. Eligible subjects will be invited to a single screening evaluation. The screening evaluation will include the following: a) obtaining an informed consent; b) tobacco use history via the Fagerstrom Test of Nicotine Dependence (FTND) and DSM-5 Tobacco Use Disorder (TUD) criteria; d) urine cotinine levels determined with a NicAlert test strip (info: www.nymox.com/default.action?itemid=47). If subjects are eligible they will be invited to participate in a second evaluation, which will include: a) complete physical and psychiatric examination including the structured clinical interview (SCID) for DSM-5 criteria; b) a complete physical and laboratory examination including CBC, TSH, ALT, AST, GGT, alkaline phosphatase, glucose, BUN and creatinine; c) urine analysis for drug screening, and for women, urine pregnancy test; and d) ECG

Inclusion criteria: 1) Female and male smokers, aged 18 to 35 years, who have been smoking tobacco cigarettes for at least a year; 2) smoke ≥ 5 and less than 20 cigarettes per day; 3) urine cotinine levels > 100 ng/mL consistent with nicotine intake of an active smoker (23); 4) not seeking treatment at the time of the study for nicotine dependence; 5) in good health as verified by medical history, screening examination, and screening laboratory tests; and 6) for women, not pregnant as determined by pregnancy screening, nor breast feeding, and using acceptable birth control methods.

Exclusion criteria: 1) history of major medical or psychiatric disorders that the physician investigator deems as contraindicated for the subject to be in the study; 2) regular use of psychotropic medication (antidepressants, antipsychotics, or anxiolytics); 3) current alcohol or substance dependence for any other recreational or prescription drugs other than nicotine; 5) use of e-cigarettes more than 10 days in the past 30 days; 6) urine drug screening indicating recent illicit drugs use (with the exception of marijuana).

Justification for age criteria: The study will enroll young adults between the ages of 18 to 35 to minimize variation in the number of years of smoking that can influence measures of dependence including withdrawal severity (24, 25).

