Justification to include smokeless tobacco and e-cigarette users: We will include users of smokeless tobacco or e-cigarettes given the high prevalence of e-cigarette and smokeless tobacco products among young adults (26-28). As noted above, urine cotinine will be used to biochemically confirm the subjects' nicotine consumption and smoking status and used as a covariate in all analyses if required.

Subject sampling to account for sex, race, dependence symptoms, and smoking frequency: We are planning to enroll Caucasian and African-American smokers while maintaining an approximately equal male-to-female ratio.

We will create dichotomous variables to be used as a covariate to match groups on race (European American and African American) and sex because of the potential influence of race and sex on smoking behavior and nicotine pharmacokinetics (22, 29). We will also control for differences in the frequency of smoking because it may influence the behavioral effects nicotine (30-32); a continuous variable based on the reported smoking frequency (cigs per day) will be used as a covariate in the analyses if required.

8: Recruitment:

Hundred subjects will be recruited. The goal is to have 70 completers, 35 menthol and 35 non-menthol cigarette smokers.

9. Research Plan:

A. Overview

Experimental Summary: Subjects will complete five separate experimental sessions on five separate days with each session beginning around 8 AM (Fig 2). Each session (1 to 15 days apart) will include one infusion condition that will be either saline or nicotine at four different infusion rates. The five infusion conditions will be assigned randomly to one of the five experimental sessions. All infusions will last 10 minutes and be controlled by two infusion pumps, a saline infusion pump and a nicotine infusion pump. The 0.24 mcg/kg/s condition will include a 1 minute infusion of nicotine followed by a 9 min infusion of saline; the 0.096 mcg/kg/s condition will include a 2.5 minute infusion followed by a 7.5 min infusion of saline; the 0.048 mcg/kg/s condition will include a 5 min infusion of nicotine followed by a 5 min infusion of saline; the 0.024 mcg/kg/s condition will include a 10 min infusion of nicotine and no infusion of saline; and the placebo condition will include a 10 min infusion of saline and no

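### Sections 8 and 10 disagree on whether 35 per group are recruited or complete, and on Section 10's own figures the menthol main effect has about 75% complete-case power, not 80%

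*Combined protocol and SAP*

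**What the plan says.** Section 7 (Subjects) opens with "One hundred smokers will be recruited from the New Haven area". Telephone contact and a screening visit with consent follow, and then: "If subjects are eligible they will be invited to participate in a second evaluation".

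Section 8 (Recruitment) repeats the 100 and sets the target: "Hundred subjects will be recruited. The goal is to have 70 completers, 35 menthol and 35 non-menthol cigarette smokers".

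Section 10 (Rationale for sample size) gives two requirements. The first is 80% power at f = 0.4 "for the main effect of menthol with 31 individuals per group at 0.025 significance level", where the 0.025 is a Bonferroni split over two outcomes. The second is 28 per group for the within-subject effect of delivery rate and for its interaction with menthol preference. The section then closes: "To account for 20% drop-out rate, we will recruit 35 participants for each group".

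For the analysis, Section 10 plans linear mixed effects models and says: "Random effects for subject and condition within subject will be used to account for correlations between repeated measures". It does not say whether participants who miss sessions are analysed.

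**The concern.** There are two faults.

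1. Thirty-five per group is the number left after drop-out in Section 8 and the number before drop-out in Section 10. The expected number of completers is therefore either 70 or 56, and the number recruited is either 100 or 70.
2. Within Section 10, the allowance for drop-out has been applied to the smaller of the two requirements. The larger one belongs to the menthol main effect.

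Menthol is in the study title, the menthol comparison is Hypothesis 1B, and Section 10 expects a significant menthol main effect. If Section 10 describes the real plan, the stated 80% power for that effect is not delivered among completers. In either case, recruitment and attrition cannot be judged against a fixed target.

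**Working it through.** **Inputs, all from Section 10 unless noted.** Effect f = 0.4, equivalent to d = 0.8 for two equal groups; alpha 0.025; power 80%; 31 per group (menthol main effect); 28 per group (rate and interaction); drop-out 20%; 35 recruited per group. From Section 8: 100 recruited, 70 completers, 35 per group. Section 10 does not state sidedness; two-sided is used because it reproduces the plan's number.

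**Step 1: reproduce the plan's 31.** Two-group comparison, noncentral t with noncentrality d × √(n/2) and 2n − 2 degrees of freedom, two-sided alpha 0.025.
- n = 31: noncentrality 0.8 × √15.5 = 3.15, power 80.0%. This matches the plan.
- Two-sided alpha 0.05, or one-sided 0.025, would need only about 26 per group, so neither is what was used.

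**Step 2: apply the plan's drop-out.**
- 35 × 0.8 = 28 per group, 56 in total. Conversely, 28 / 0.8 = 35 exactly, so the inflation was built on the 28.
- The larger requirement would need 31 / 0.8 = 38.75, so 39.
- With 35 starting, the loss that still leaves 31 is (35 − 31) / 35 = 11.4%, against the 20% assumed.

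**Step 3: menthol main-effect power under each reading (same method as Step 1).**

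| Reading | Completers per group | Power at d = 0.8 | d detectable with 80% power |
|---|---|---|---|
| Section 10: 35 recruited, 20% lost | 28 | 75% | 0.84 |
| Stated requirement | 31 | 80% | 0.80 |
| Section 8: 35 complete | 35 | 85% | 0.75 |

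**Step 4: compare the losses.** Section 8 goes from 100 to 70, a loss of 30%; Section 10 assumes 20%. If 20% is kept and 35 per group are to complete, 35 / 0.8 = 43.75, so 44 per group (88 in total) must start sessions, which leaves 100 − 88 = 12 for loss at screening.

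**Step 5: let drop-outs contribute to the mixed model.** Assume that the 7 drop-outs per group each give k of the five sessions, spread evenly over conditions and missing at random, with equal correlation ρ between sessions and d = 0.8 on the five-session mean. The effective number per group is

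n_eff = 28 + 7k(1 + 4ρ) / {5[1 + (k − 1)ρ]}.

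Power uses this n_eff with 68 degrees of freedom (70 participants, two groups).

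| ρ | k = 1: n_eff, power | k = 2: n_eff, power |
|---|---|---|
| 0.3 | 31.1, 80.3% | 32.7, 82.5% |
| 0.5 | 32.2, 81.8% | 33.6, 83.6% |
| 0.7 | 33.3, 83.2% | 34.3, 84.3% |

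The documents give neither ρ nor the timing of drop-out, so these are illustrations over a range. If drop-outs give no session, n_eff returns to 28 and power to 75%.

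**The case against.** The strongest reply has three parts.

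- **Recruited may mean two things.** In Section 7 the word covers people reached by advertisement who still face two evaluations; in Section 10 it may mean people who enter sessions. On that reading 100 and 70 can coexist. This stands for 100 against 70. It does not explain how 35 per group can be both completers and the number taken on to absorb drop-out.
- **Section 8 may govern.** It is the dedicated recruitment section, and its 35 completers per group exceed 31. This also stands: under Section 8 there is no shortfall and power is about 85%. But the power statement and the drop-out allowance sit in Section 10, and they do not agree with each other.
- **75% is not the power of the planned model.** No complete-case rule is stated, and in every scenario in Step 5 power is at least 80%. So 75% is a floor, and a shortfall in the actual analysis has not been shown. However, Section 10 sets its requirements in individuals per group and inflates for loss, which treats drop-outs as contributing nothing, and nothing in the plan says that they will contribute.

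It is also fair to say that the 28 / 0.8 = 35 arithmetic is correct for the sentence it follows. The fault is that the larger requirement was not carried through. Whether 28 per group is enough for the rate and interaction effects was not rechecked, because no within-subject correlation is given; the plan's figure is taken as stated.

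**Conclusion.** The concern holds. The two sections contradict each other on whether 35 per group is a count before or after drop-out. Section 10 also fails its own requirement for the menthol main effect: 28 per group against 31, or about 75% complete-case power against the stated 80%, with the detectable effect rising from d = 0.80 to 0.84. That figure rests on d = 0.8, two-sided alpha 0.025, exactly 20% drop-out and no data from drop-outs. The shortfall is modest, applies only if Section 10 is the real plan, and is confined to the menthol main effect as far as the stated requirements go. The contradiction itself does not depend on any of these assumptions and should be corrected.

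**What to change.** Decide which section describes the plan and put the same numbers in Sections 7, 8 and 10, using separate words for those recruited or screened, those who start sessions, and those who complete.

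- **If Section 8 is the plan,** replace the last sentence of the sample-size rationale with text such as: *One hundred smokers will be recruited to obtain 35 completers per group. With 35 completers per group, power for the menthol main effect is about 85% for d = 0.8 at two-sided alpha 0.025.* Add how the loss from 100 to 70 divides between screening and drop-out. If 20% drop-out is kept, that means 44 per group starting sessions and 12 of the 100 lost before then.
- **If 35 per group is the number taken on before drop-out,** correct Section 8 to about 28 completers per group and Sections 7 and 8 to 70 recruited (or say that the 100 are people screened). Restate menthol main-effect power as about 75% among completers, with a detectable d of 0.84.

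In both cases, state whether participants with some but not all sessions enter the mixed model. Any claim of power above the complete-case figure should give the assumed correlation between sessions and timing of drop-out.

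Either route is a change of wording. It adds no participants and alters no outcome, analysis or procedure.

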Confidentiality will be protected by having records identified by code number only with the master list including names kept in a sealed envelope in a locked file in the Principal Investigator's office and by the pharmacy. Subjects will be given telephone numbers to call in case of emergency, 24 hours a day.

12.1 Potential benefits of the proposed research to the subjects and others. There will be no direct benefit to subjects participating in this study. However, subjects will receive complete medical and psychological evaluation. Cigarette smokers will be given anti-smoking literature and treatment resources will be provided for smoking cessation.

12.2 Importance of the knowledge to be gained. This proposed study may help to develop new and more effective tobacco control policies. We believe that the risk/benefit ratio for this study is acceptable, and that the benefits of the proposed studies outweigh the potential risks to subjects.

12.3 Data safety and monitoring plan: The Principal Investigator will conduct a review of all adverse events and determine the attribution and grade of severity of the adverse event by using the following scales:

Attribution of Risk Categories:

Definite: Adverse event(s) will clearly be related to investigational agent(s) or other intervention

Probable: Adverse event(s) will likely be related to investigational agent(s)

Possible: Adverse event(s) may be related to investigational agent(s)

Unlikely: Adverse event(s) will doubtfully be related to investigational agent(s)

Unrelated: Adverse event(s) will clearly not be related to the investigational agents(s)

Grades of Risk:

0: No adverse event or within normal limits

1: Mild adverse event

2: Moderate adverse event

3: Severe adverse event resulting in hospitalization or prolongation of existing hospitalization, a persistent or significant disability/incapacity, or a congenital anomaly/birth defect

4: Life-threatening or disabling adverse event

5: Fatal adverse event

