Serious adverse events (SAEs) include any untoward medical occurrence that at any dose results in death or the immediate risk of death, hospitalization or the prolonging of an existing hospitalization, persistent or significant disability/incapacity or a congenital anomaly/birth defect. Subjects will be terminated from participation if the investigator feels that subjects' health or well-being may be threatened by continuation in the study. Serious unanticipated and anticipated adverse events will be reported within 48 hours to the VA Hospital and Yale IRB, and NIDA. We will directly report to the FDA, whenever their magnitude or frequency exceeds expectations.

The risk associated with participating in this study is moderate, because nicotine administered may be associated with mild side effects. Serious side effects associated with this treatment are not expected. This project will be monitored by a Data and Safety Monitoring Board (DSMB) because the study involves double-blind treatment of smokers with nicotine. This board is composed of persons not otherwise affiliated with the clinical study who are experienced in various aspects of the conduct of clinical trials for the treatment of addictive disorders. We propose three investigators located here in Connecticut who are not directly involved in this study – [name]., [name]., and [name]. as the members of the DSMB. The members of the DSMB and all study Investigators will complete Conflict of Interest forms created by Yale's IRB in accordance with NIH guidelines.

In order for the DSMB to fulfill its mission of assuring the safety of human subjects and the scientific integrity of the studies conducted, the Board will have access to accumulating study outcome data in a manner that will protect its confidentiality and preserve its statistical integrity. The Board will examine accumulating data to assure that the risks and benefits of participation remain acceptable and that the results of the study will be considered scientifically reliable. The conditions under which the Board will examine this data are described below. This monitoring will be consistent with NIH policy regarding the protection of human subjects in research, and FDA guidance on statistical practices for clinical trials (ICH E9) and good clinical practices (ICH E6). In general, the data to be reviewed will include screening data, baseline data, efficacy data, and safety data.

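### Grade 3 of the adverse-event scale requires a serious-event outcome, so a severe event without one has no matching grade, and disability fits both grade 3 and grade 4

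*Combined protocol and SAP*

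**What the plan says.** Section 12.3 (Data safety and monitoring plan) has the Principal Investigator review all adverse events and "determine the attribution and grade of severity of the adverse event by using the following scales". The Grades of Risk list runs from 0 (no event) to 5:

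- Grade 1: "1: Mild adverse event"
- Grade 2: "2: Moderate adverse event"
- Grade 3: "Severe adverse event resulting in hospitalization or prolongation of existing hospitalization, a persistent or significant disability/incapacity", or a birth defect
- Grade 4: "4: Life-threatening or disabling adverse event"
- Grade 5: "5: Fatal adverse event"

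Grades 1 and 2 carry no criteria beyond the adjective.

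The next paragraph of Section 12.3 defines serious adverse events. Besides death and immediate risk of death, it lists "hospitalization or the prolonging of an existing hospitalization, persistent or significant disability/incapacity or a congenital anomaly/birth defect". Reporting to the hospital, the IRB and NIDA within 48 hours is tied to that definition.

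No other severity scale appears in the document. The SAFTEE (Section 9.C.2, item 6) is given before and after each session, but no grading rule is attached to it.

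**The concern.** Severity is the intensity of an event. Seriousness is its outcome. The scale is offered as a measure of severity, but from grade 3 upwards it is defined mainly by outcome. This has two consequences.

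The first is a gap. An intense reaction that resolves in the laboratory without admission, lasting harm or threat to life is severe in the ordinary sense, but it does not meet grade 3. The highest grade that asks for no such outcome is moderate.

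The second is an overlap. Disability is a criterion for grade 3 and again for grade 4, so two assessors could grade the same event differently and both be following the protocol.

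What is at stake is how informative the safety record is. Grades 3 to 5 largely repeat the serious-event flag. Non-serious events are left with two undefined levels, and Section 12.3 says that serious side effects are not expected. The scale therefore separates events least well where most of them should fall.

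**Working it through.** No numerical design input is involved and the plan gives no figure to reproduce. The check takes each kind of severe event and reads it against the Grades of Risk list and the serious-event definition, both in Section 12.3.

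| Severe event that… | Grade(s) met | Serious? |
|---|---|---|
| leads to admission or a longer stay | 3 | yes |
| causes lasting or significant disability, without admission | 3 and 4 | yes |
| involves a birth defect, without admission | 3 | yes |
| is life-threatening, without admission | 4 | yes |
| is fatal | 5 | yes |
| has none of these outcomes | none | no |

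**The gap (last row).** Grade 3 requires both that the event is severe and that one of three outcomes follows. All three are among the serious-event criteria. If no listed outcome occurs, grade 3 fails on its second requirement and grades 4 and 5 do not apply. Grade 2 does not strictly apply either, since the event is not moderate. The event has no matching grade, and grade 2 is the likely default because it is the highest level that requires no outcome.

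**Whether the protocol foresees such events.** Sections 9.B and 12 provide for stopping when blood pressure or heart rate passes stated limits or signs of nicotine toxicity appear. An event of that kind could be judged severe, end a session and settle without admission. It would then sit in the last row.

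**The overlap (second row).** Grade 4 uses the word disabling without defining it, so a lasting or significant disability satisfies it as well as grade 3. An unstated convention of assigning the highest applicable grade would send such events to grade 4, but the disability criterion in grade 3 would then do no work. The two definitions need an explicit boundary either way.

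**What depends on the grade.** The 48-hour reporting rule uses seriousness. Termination uses vital signs and toxicity signs (Sections 9.B and 12) or the investigator's judgement about the participant's well-being (Section 12.3). Section 10 plans no analysis of grade. What remains is the severity record itself and any summary by grade shown to the Data and Safety Monitoring Board, which meets three times a year and is presented with the adverse events.

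**The case against.** The strongest reply is that nothing in the conduct of the trial turns on the grade. Reporting and termination run on other criteria, the board reviews safety data and not grades alone, and a disability of the kind named in grade 3 is a serious event whichever grade it receives. Tolerability is also captured by repeated heart rate and blood pressure readings, by Drug Effects Questionnaire items such as bad effects and anxiety, and by the SAFTEE. All of this stands, and it limits the point to the quality of the severity record.

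A second reply is that few events will be affected. Section 11 ties the listed toxic effects to doses 10 to 20 times those planned and reports no adverse events from nicotine in more than 100 smokers. Section 9.A describes the fastest rate as well tolerated. These are the investigators' own statements, but they are the only evidence in the document. This also stands.

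A reader might infer more than the text supports:

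- *Every severe event without admission must be graded moderate.* It need not be. Such an event can be grade 3 through disability or birth defect, grade 4 if life-threatening or disabling, or grade 5 if fatal.
- *Affected events are always recorded a grade too low.* Nothing instructs the investigator to choose grade 2, and some might choose grade 3 on the word severe. The defect is a missing category with a probable default, not a demonstrated downgrade.
- *Reactions to the fastest infusion are hidden, or a severity gradient across rates is flattened.* The document does not say that severe non-serious reactions are likely after rapid infusion, and it plans no comparison of grade by infusion condition.

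None of this supplies the missing grade or separates grade 3 from grade 4.

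**Conclusion.** The point holds in a limited form. Applied as written, the scale has no grade for a severe event that lacks a serious outcome, and it gives two grades to one that causes lasting or significant disability. These are faults in a stated rule, not details left for later, and no other section repairs them.

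The size cannot be put as a number because the document gives no frequency of severe non-serious or disabling events. It may well be small. No endpoint, power figure, reporting deadline or termination criterion is affected. The conclusion rests on two readings: that grade 3 means what it says in requiring a listed outcome, and that an investigator facing an ungraded severe event would usually settle on grade 2. The second is a judgement. If it is wrong, the result is inconsistent grading instead of under-grading, and the correction is the same.

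**What to change.** Rewrite the Grades of Risk list in Section 12.3 so that each event has exactly one grade:

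- Grades 1, 2 and 3: mild, moderate and severe, defined by intensity only, with a short descriptor for each. Grade 3 means severe but not life-threatening.
- Grade 4: life-threatening but not fatal.
- Grade 5: fatal.
- Remove admission, disability and birth defect from the grades.

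Add a separate yes/no field for seriousness, completed with the definition already in Section 12.3. That definition and the reporting timelines stay as they are.

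Keeping disability in the scale with a stated boundary between grades 3 and 4 would cure the overlap but not the gap, so grading by intensity is the simpler repair. The cost is a few lines of protocol wording and one extra field on the adverse-event form.
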